5.2.4. Analyses for Time to Event Data

The ... time to treatment withdrawal due to lack of efficacy will also be analyzed for discontinuation up to Week 16 (end of treatment period). The time to discontinuation will be analyzed using the log-rank test, with Kaplan-Meier estimates of the time to discontinuation shown for selected percentiles, dependent on the level of discontinuation. The expectation is that these would be the 1st, 2nd, 5th, 10th and 25th percentiles, in addition to the minimum and maximum time to discontinuation. Other percentiles may be shown if the level of discontinuation due to lack of efficacy as calculated using Kaplan-Meier procedure is sufficiently large.

A plot of the time to discontinuation (failure) will be shown using the Kaplan-Meier estimates. Only treatment discontinuation up to the end of treatment period (Week 16 visit or early discontinuation) will be used in this analysis. Discontinuation due to lack of efficacy after the end of treatment visit will be included in the standard safety tables. Time to event for discontinued subjects (discontinuing for reasons other than lack of efficacy) prior to the Week 16 visit uses censoring at the time of discontinuation. Imputation of time to event for completed subjects or discontinued subjects (for any reason) post Week 16 visit uses censoring at the Week 16 visit time point.

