2.2. Study Design

The study design is summarized in the diagram below.

Figure 1. Study Design

This is a randomized, double-blind, placebo-controlled, multicenter, parallel-group, Phase 3 study of the efficacy and safety of tanezumab when administered by SC injection for 16 weeks compared to placebo in subjects with osteoarthritis of the knee or hip. Approximately 690 subjects (approximately 230 per treatment group) will be randomized to one of 3 treatment groups in a 1:1:1 ratio. Subjects will receive a total of two SC injections, separated by 8 weeks:

- *tanezumab 2.5 mg (Day 1) and tanezumab 2.5 mg (Week 8);*
- *tanezumab 2.5 mg (Day 1), and tanezumab 5 mg (Week 8);*
- *placebo to match tanezumab (Day 1) and placebo to match tanezumab (Week 8).*

The randomization will be stratified by the factors of index joint and highest Kellgren-Lawrence grade in the knee and hip joints.

This study is designed with a total (post-randomization) duration of 40 weeks and will consist of three periods: Screening (up to a maximum of 37 days), Double-blind Treatment (16 weeks, 6 in-clinic visits), and Safety Follow-up (24 weeks). The Screening Period (to begin up to 37 days prior to Randomization) includes a Washout Period (lasting a minimum of 2 days for all prohibited pain medications) if required, and an Initial Pain Assessment Period (IPAP; 7 days prior to Randomization/Baseline; minimum 3 days).

The end of treatment period is at Week 16, with the safety follow-up period up to Week 40. The primary time point for efficacy is Week 16. The period of interest for most safety results is the treatment period. Selected safety results will also be provided separately for the safety follow-up period, and some results will be provided for the combined overall study period comprising the treatment and safety follow-up periods.

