5.1.2. Statistical Decision Rules

The Type I error rate (α -level) used in the assessment of pair-wise treatment comparisons for the primary efficacy endpoints is 5%. The fixed sequence testing strategy of the co-primary endpoints is described below.

The assessment of significance for the tanezumab versus placebo treatment contrasts will use a step-down testing strategy within each of the co-primary efficacy endpoints. The step-down testing will first test tanezumab 2.5/5 mg versus placebo, and if statistically significant ($p \leq 0.05$) will then test tanezumab 2.5 mg versus placebo. Finally, the particular tanezumab dose group is declared as superior to placebo if the corresponding treatment contrast is significant over all three co-primary endpoints. This testing procedure will maintain the Type I error to 5% or less within each of the co-primary efficacy endpoints, and to less than 5% for all three co-primary efficacy endpoints.

The secondary endpoint of subjects with $\geq 50\%$ reduction from baseline in WOMAC Pain at Week 16 is identified as a key secondary endpoint and will be included in the testing strategy. If both tanezumab regimens are found to be statistically significantly better than placebo in the primary comparisons described above, the two comparisons of this secondary endpoint (tanezumab 2.5 mg treatment group versus placebo and tanezumab 2.5/5 mg treatment group versus placebo) will be adjusted for multiple comparisons using the Hochberg procedure and an overall significance level of 0.05.

The primary analysis will be that with the multiple imputation approach (see below for details), and thus the overall type I error is controlled for each of the two dose regimens (2.5 mg and 2.5/5 mg) since all three co-primary endpoints need to be significant for a single dose. The overall type I error of the study is also controlled given the step-down testing strategy for each of the primary endpoints and the key secondary endpoint. Control of the type I error rate accounting for multiplicity of contrasts will only apply to the three co-primary endpoints (model with the primary imputation analysis) and the key secondary endpoint.

Regardless of the outcome of the primary and key secondary analyses, the secondary endpoints will be tested. No adjustment for multiple comparisons will be made for the secondary efficacy, and for the safety endpoints. The α -level for each hypothesis test for the secondary and exploratory analyses will be 5%.

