The incidence ... of use of rescue medication... will be analyzed for Weeks 2, 4, 8, 12, and 16... The incidence of use of rescue medication will be analyzed using logistic regression for binary data, with model terms for Baseline WOMAC Pain subscale score, Baseline diary average pain, index joint, Kellgren-Lawrence grade, and treatment group. ... Estimated levels of rescue medication use will be shown for each treatment group, and the ratio (with

95% CI) for comparisons versus placebo will be shown. Imputation for missing rescue medication data will use LOCF only.

The incidence of treatment withdrawal due to lack of efficacy ('Insufficient Clinical Response' on the Subject Summary Case Report form) will also be analyzed for discontinuation up to Week 16 (end of treatment period). The analysis of the incidence of discontinuation due to lack of efficacy will be made using logistic regression for binary data, with model terms for Baseline WOMAC Pain subscale score, Baseline diary average pain score, index joint, Kellgren-Lawrence grade, and treatment group. Discontinuation in the post-treatment safety follow-up period will not be included in this endpoint for analysis, but will be summarized as part of the safety tables.

Cumulative WOMAC Pain response and WOMAC Physical Function at Week 16 using response definitions from a reduction of >0% to =100% (in steps of 10%) will be summarized, using mixed BOCF/LOCF (as described above), and also LOCF and BOCF imputation for WOMAC Pain and WOMAC physical function. Imputation with BOCF for subjects with missing data at that timepoint will lead to the subjects being assessed as non-responders for the response endpoint.

The proportion of subjects who meet a WOMAC Pain response definition at Week 16 will be examined in the cohort of subjects who had a WOMAC Pain response to treatment at Week 8 and the cohort of subjects who did not have a WOMAC Pain response at Week 8. Treatment comparisons will be made within each cohort for tanezumab 2.5/5 mg versus placebo and tanezumab 2.5 mg versus placebo. A descriptive comparison will also be made between the treatment groups of tanezumab 2.5/5 mg versus tanezumab 2.5 mg. These analyses will be produced for the WOMAC Pain response levels of 30% and 50%, and other response definitions (15%). This is an exploratory analysis as treatment comparisons are not specifically powered to achieve significance within cohorts of subjects.

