Reduction of >0%, ≥10%, to ≥90% (in steps of 10%) and =100% from Baseline to Week 16 in the WOMAC Physical Function subscale	ITT	None (summary)	NA	BOCF	Summary of secondary endpoint
Reduction of >0%, ≥10%, to ≥90% (in steps of 10%) and =100% from Baseline to Week 16 in the WOMAC Physical Function subscale	ITT	None (summary)	NA	LOCF	Summary of secondary endpoint
Change from Baseline to Weeks 2, 4, 8, 12, and 16 in the WOMAC Stiffness subscale	ITT	ANCOVA	BL Score, BL diary average pain, Index Joint (Knee/Hip), Highest KL grade (2, 3 or 4), Treatment Group (Study site as a random effect)	Multiple Imputation	Secondary Endpoint Analysis
Change from Baseline to Weeks 2, 4, 8, 12, and 16 in the WOMAC Average Score	ITT	ANCOVA	BL Score, BL diary average pain, Index Joint (Knee/Hip), Highest KL grade (2, 3 or 4), Treatment Group (Study site as a random effect)	Multiple Imputation	Secondary Endpoint Analysis
Change from Baseline to Weeks 2, 4, 8, 12, and 16 in the WOMAC Item: Pain When Walking on a Flat Surface	ITT	ANCOVA	BL Score, BL diary average pain, Index Joint (Knee/Hip), Highest KL grade (2, 3 or 4), Treatment Group (Study site as a random effect)	Multiple Imputation	Secondary Endpoint Analysis
Change from Baseline to Weeks 2, 4, 8, 12, and 16 in the WOMAC Item: Pain When Going Up or Down Stairs	ITT	ANCOVA	BL Score, BL diary average pain, Index Joint (Knee/Hip), Highest KL grade (2, 3 or 4), Treatment Group (Study site as a random effect)	Multiple Imputation	Secondary Endpoint Analysis
Change from Baseline to Days 1, 2, 3, 4, 5, 6, 7, and to Weeks 1, 2, 3, 4, 6, 8, 10, 12, and 16 in the weekly average pain score in the index joint	ITT	ANCOVA	BL Score, Index Joint (Knee/Hip), Highest KL grade (2, 3 or 4), Treatment Group (Study site as a random effect)	Multiple Imputation	Secondary Endpoint Analysis

Time to treatment discontinuation due to lack of efficacy (up to Week 16)	ITT	Log-Rank (with KM estimates)	Treatment Group	Observed	Secondary Endpoint Analysis
Incidence of treatment discontinuation due to lack of efficacy (up to Week 16)	ITT	Logistic Regression	BL WOMAC Pain, BL diary average pain, Index Joint (Knee/Hip), Highest KL grade (2, 3 or 4), Treatment Group	Observed	Secondary Endpoint Analysis
Incidence of rescue medication use during Weeks 2, 4, 8, 12, and 16	ITT	Logistic Regression	BL WOMAC Pain, BL diary average pain, Index Joint (Knee/Hip), Highest KL grade (2, 3 or 4), Treatment Group	LOCF	Secondary Endpoint Analysis

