Number of days of rescue medication use during Weeks 2, 4, 8, 12, and 16	ITT	Negative Binomial Model	BL WOMAC Pain, BL diary average pain, Index Joint (Knee/Hip), Highest KL grade (2, 3 or 4), Treatment Group	LOCF	Secondary Endpoint Analysis
Amount (mg) of rescue medication taken during Weeks 2, 4, 8, 12, and 16	ITT	Negative Binomial Model	BL WOMAC Pain, BL diary average pain, Index Joint (Knee/Hip), Highest KL grade (2, 3 or 4), Treatment Group	LOCF	Secondary Endpoint Analysis
EQ-5D-5L dimensions (Mobility; Self-care; Usual activities; Pain/Discomfort; Anxiety/Depression), EQ-VAS and Overall Health Utility at Baseline and Weeks 8 and 16	ITT	Summary	NA	Observed	Secondary Endpoint Analysis
WPAI endpoints (% work time missed; % impairment while working; % overall work impairment; % activity impairment) at Week 16	ITT	ANCOVA	BL score, BL diary average pain, Index Joint (Knee/Hip), Highest KL grade (2, 3 or 4), Treatment Group (study site as a random effect)	Observed	Secondary Endpoint Analysis
Healthcare Resource Utilization at Baseline, Weeks 24 and 40	ITT	Descriptive Summary	Treatment group	Observed	Secondary Endpoint Analysis
Change from baseline to Weeks 2, 4, 8, 12, 16, 24, and 40 in the NIS score, and Change from Baseline to Worst post-Baseline NIS score	ITT	CMH test	Treatment Group [1]	LOCF (Weeks 2, 4, 8, 12, 16, 24, & 40), Worst post-baseline score	Safety Endpoint Analysis
Survey of Autonomic Symptoms (SAS), number of symptoms and total impact score (by visit and change from Baseline)	ITT	Summary	NA	Observed	Safety Endpoint Analysis

[1] CMH test will be stratified by the levels of the combined stratification parameters (6 levels). If there are <15 subjects in any combined stratification level then the CMH test will be unstratified

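### The log-rank test for time to discontinuation due to lack of efficacy is the only inferential efficacy analysis in the SAP that leaves out the randomisation strata; the test is valid, and the cost is a small loss of efficiency at most

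*SAP*

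**What the plan says.** Section 2.2 sets the design: "The randomization will be stratified by the factors of index joint and highest Kellgren-Lawrence grade in the knee and hip joints". With two joints and three grades, that gives 2 x 3 = 6 cells.

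Section 5.2.4 covers time to treatment withdrawal for lack of efficacy up to Week 16: "The time to discontinuation will be analyzed using the log-rank test". The word unstratified does not appear there. It follows from Appendix 1, where the row marked "Log-Rank (with KM estimates" has treatment group as its only entry under model and covariates. That row also lacks the footnote attached to the CMH rows, which reads "CMH test will be stratified by the levels of the combined stratification parameters (6 levels".

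The incidence of the same event is handled in Section 5.2.1: "The analysis of the incidence of discontinuation due to lack of efficacy will be made using logistic regression for binary data". Both stratification factors enter that model, next to two baseline pain measures and the randomised arm. Section 5.1.2 places the endpoint outside the controlled family: "No adjustment for multiple comparisons will be made for the secondary efficacy, and for the safety endpoints". Each secondary test is run at 5%.

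Section 3.4.1 says that analysis models use the strata entered at randomisation. That settles which source of stratum values applies; it does not bring strata into the log-rank test.

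**The concern.** The SAP follows a consistent convention of analysing as randomised, and this one test departs from it without giving a reason. When strata are prognostic and balanced by design, a test that ignores them uses a variance that is somewhat too large. It then rejects slightly too seldom under the null and loses some power under the alternative. At stake is the efficiency of one secondary test, and the ease of explaining why it alone sets the strata aside.

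**Working it through.** **1. Is it the only exception?** Inferential efficacy rows of Appendix 1, by method:

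| Method | Index joint and K-L grade accounted for? |
|---|---|
| ANCOVA (including WPAI and interaction rows) | Yes, model terms |
| MMRM | Yes, model terms |
| Logistic regression (including incidence of this event) | Yes, model terms |
| Negative binomial | Yes, model terms |
| CMH | Yes, six combinations, with a sparse-cell fallback |
| Log-rank | No |

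**2. Is there a figure to reproduce?** No. The SAP gives no event count, rate, hazard ratio or power for this endpoint. It does give about 230 per arm and two-sided tests.

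**3. Information under assumed rates.** Assumed: placebo event proportion p of 5%, 10% or 20%, and hazard ratio (HR) 0.5. Events in one pairwise comparison: d = 230p + 230[1 - (1 - p)^0.5]. Schoenfeld power: Φ(|ln HR| x √(d/4) - 1.96).

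- p = 5%: d = 11.5 + 5.8 = 17.3; power 30%
- p = 10%: d = 23.0 + 11.8 = 34.8; power 53%
- p = 20%: d = 46.0 + 24.3 = 70.3; power 83%

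**4. Unstratified against six-stratum log-rank, by simulation.** 4000 runs per scenario, two arms of 230, balanced within strata, 112 days, two-sided 0.05. Also assumed: hip share 15%; K-L 2/3/4 shares 25/40/35%; other-cause dropout about 10%; HR between lowest and highest K-L grade of 1, 2 or 4, with hip adding half that log-HR. Power at HR 0.5:

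| Placebo rate | K-L HR | Unstratified | Stratified | Change (points) |
|---|---|---|---|---|
| 5% | 1 | 26.1% | 26.0% | -0.1 |
| 5% | 2 | 27.5% | 27.7% | +0.2 |
| 5% | 4 | 30.7% | 31.1% | +0.4 |
| 10% | 1 | 49.0% | 49.2% | +0.2 |
| 10% | 2 | 51.4% | 51.3% | -0.1 |
| 10% | 4 | 55.3% | 55.8% | +0.5 |
| 20% | 1 | 79.6% | 79.5% | -0.1 |
| 20% | 2 | 80.9% | 81.1% | +0.2 |
| 20% | 4 | 81.9% | 83.7% | +1.8 |

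Type I error ran from 4.2% to 5.1% unstratified and from 4.4% to 5.0% stratified. In the most prognostic scenario (20%, K-L HR 4) it was 4.2% against 4.7%. The Monte Carlo standard error near 5% is √(0.05 x 0.95/4000) = 0.34 points, so that conservatism is modest.

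**5. Sparse cells.** With smaller shares (hip 15%, K-L 2 15%), the hip/K-L 2 cell is 0.15 x 0.15 = 2.25% of subjects: 0.0225 x 460 = about 10 in a pairwise comparison, and 0.0225 x 690 = about 15.5 over three arms. A simulation with a cell of about 10 in 460 gave power changes of -0.3 to +1.6 points, with type I error near 5% for both tests. Stratifying carries no material penalty because each event is compared with the risk set of its own stratum, and a small cell adds few events to either the numerator or the variance.

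**The case against.** The strongest reply is that nothing here is wrong. Section 5.2.4 and Appendix 1 agree with each other, the test is fully specified, and an unstratified log-rank after stratified randomisation is valid. The power gain is close to zero in most scenarios. It depends on event rates, prognostic effects and stratum shares that the SAP does not give. Small cells could also trigger the SAP's own rule for CMH tests, which drops stratification when any of the six combinations has fewer than 15 subjects. In the small-share example above, about 10 subjects in a pairwise comparison would fall under that limit, while about 15.5 over three arms would just pass.

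Much of this stands. A reader might infer that the test is invalid or inflates type I error; the simulated error rates show neither. A reader might infer that the SAP contradicts itself; no section promises a stratified log-rank. A reader might also infer that stratifying would make the two analyses of this event condition on the same factors. It would not, because the logistic model also includes Baseline WOMAC Pain and Baseline diary average pain.

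What the reply does not remove is that this is the one inferential efficacy row out of line with the randomisation, without explanation. Sparseness does not justify the omission, since the existing CMH fallback can cover it.

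**Conclusion.** The point holds as a minor improvement. The log-rank test is valid but ignores factors that were balanced by design. If those factors are strongly prognostic, it is slightly conservative and gives up about 0 to 2 points of power. The clear gain appears only with strong prognostic strata: +1.8 points at a 20% placebo rate and a K-L hazard ratio of about 4. Otherwise the change is within about half a point in the main set of scenarios. These sizes rest on the assumed event rates, hazard ratio, stratum shares and dropout. The endpoint is secondary and carries no multiplicity control, so the co-primary and key secondary conclusions do not depend on it.

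**What to change.** In Section 5.2.4 and in the corresponding Appendix 1 row, specify a log-rank test stratified by the six combinations of index joint and highest K-L grade, using the strata entered at randomisation as Section 3.4.1 does for the models. Add the CMH fallback: unstratified if any of the six combinations has fewer than 15 subjects. State whether that count is taken over all three arms or within each comparison, since the answer could decide which test is run. Keep the Kaplan-Meier estimates and plots unstratified.

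The cost is a sentence in Section 5.2.4, an amended table row with the fallback rule, and one procedure option in the program. No data collection or sample size changes.

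### The Kaplan-Meier curve and upper percentiles for discontinuation due to lack of efficacy treat other withdrawals as ordinary censoring and so modestly overstate the actual cumulative probability

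*SAP*

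**What the plan says.** Section 5.2.4 defines the endpoint: "time to treatment withdrawal due to lack of efficacy will also be analyzed for discontinuation up to Week 16 (end of treatment period". The method follows: "The time to discontinuation will be analyzed using the log-rank test, with Kaplan-Meier estimates". On percentiles it says "The expectation is that these would be the 1st, 2nd, 5th, 10th and 25th percentiles", together with the minimum and maximum; further percentiles may be added if the Kaplan-Meier level of LoE discontinuation is large enough. On the figure: "A plot of the time to discontinuation (failure) will be shown using the Kaplan-Meier estimates".

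There are two censoring rules. For subjects who discontinue before Week 16 for another reason, the text reads "discontinuing for reasons other than lack of efficacy) prior to the Week 16 visit uses censoring at the time of discontinuation". For completers, and for anyone who discontinues after the Week 16 visit, the analysis "uses censoring at the Week 16 visit time point". The Appendix 1 row for time to LoE discontinuation repeats log-rank with Kaplan-Meier estimates. No cumulative incidence or other competing-risk method appears in the SAP, and the curve is not labelled as a hypothetical quantity.

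Two other planned outputs cover the same event. Section 5.2.1 states "The analysis of the incidence of discontinuation due to lack of efficacy will be made using logistic regression for binary data", with number and percentage shown; the matching Appendix 1 row is headed "Incidence of treatment discontinuation due to lack of efficacy (up to Week 16" and uses the ITT set. Section 6.6 plans a table of discontinuation by treatment group, reason and study-week interval.

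**The concern.** Kaplan-Meier handles a censored subject as someone who stays at risk and whose later experience resembles that of those still under observation. This suits a completer censored at Week 16. It does not suit a subject who has stopped for an adverse event, death or another reason, because that subject can no longer stop for LoE. In effect, Kaplan-Meier gives each departed subject the later LoE risk of those who remain.

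The failure curve then answers a hypothetical question: how many would have stopped for LoE had nobody left for another reason. Section 5.2.4 nevertheless uses the Kaplan-Meier result as the level of LoE discontinuation, since that level decides which percentiles are shown. A reader will naturally take the curve as the share of subjects who stopped for LoE by a given time, and the curve is biased upward for that share.

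**Working it through.** **No figure to reproduce.** The SAP states no LoE rate, no other-withdrawal rate and no power for this endpoint. All rates below are assumptions. From the SAP come the censoring rule, the listed percentiles and about 230 subjects per arm (Section 2.2).

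**Formulas.** Let L be the actual proportion who stop for LoE by Week 16 and O the proportion who leave earlier for any other reason, with constant hazards over 16 weeks (16 × 7 = 112 days).

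- Total cumulative hazard: H = −ln(1 − L − O)
- LoE part: h = H × L/(L + O)
- Planned estimate at Week 16: 1 − KM = 1 − exp(−h)
- Cumulative incidence function (CIF) at Week 16: L, by construction
- Day on which KM reaches percentile q: 112 × [−ln(1 − q)]/h
- Day on which the CIF reaches q: 112 × [−ln(1 − q(L + O)/L)]/H

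**Worked example, L = 10%, O = 15%.** H = −ln(0.75) = 0.2877; h = 0.2877 × 10/25 = 0.1151; 1 − KM = 1 − exp(−0.1151) = 10.87%. The excess is 0.87 points.

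**Week 16 level.**

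| L | O | 1 − KM | Excess (points) |
|---|---|---|---|
| 5% | 10% | 5.27% | 0.27 |
| 8% | 12% | 8.54% | 0.54 |
| 10% | 10% | 10.56% | 0.56 |
| 10% | 15% | 10.87% | 0.87 |
| 10% | 20% | 11.21% | 1.21 |
| 10% | 30% | 11.99% | 1.99 |

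Over a wide assumed range (L 2-25%, O 5-30%) the excess runs from 0.05 to 5.4 points, or 2.6% to 22% in relative terms. The top of that range needs 25% LoE with 30% other withdrawals.

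**Percentiles (day reached, KM against CIF).**

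| L, O | 1st | 2nd | 5th | 10th |
|---|---|---|---|---|
| 5%, 10% | 20.8 / 21.0 | 41.8 / 42.6 | 106.0 / 112.0 | not reached |
| 10%, 10% | 10.1 / 10.1 | 20.3 / 20.5 | 51.5 / 52.9 | 105.8 / 112.0 |
| 10%, 20% | 9.5 / 9.6 | 19.0 / 19.4 | 48.3 / 51.0 | 99.3 / 112.0 |

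The 25th percentile is not reached in any of these rows. The 1st and 2nd move by less than a day.

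**Effect on which percentiles appear.** With L = 9.5% and O = 15%: H = −ln(0.755) = 0.2810; h = 0.2810 × 9.5/24.5 = 0.1090; 1 − KM = 10.3%. A 10th percentile would be tabulated although fewer than 10% stopped for LoE.

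**Timing.** A simulation of one arm of 230 with 23 LoE exits (crude 10.0%) and 35 other exits gave a mean 1 − KM of 11.8% when other exits fell in the first half and LoE exits in the second, 10.9% when both were uniform, and 10.0% when all LoE exits came first. The two estimates agree only if no other withdrawal precedes the last LoE exit.

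**The case against.** The strongest reply is that the actual share is already reported. Section 6.6 tabulates discontinuation by reason and study week, and Section 5.2.1 gives the number and percentage at Week 16. The censoring rule is explicit and agrees with Appendix 1. The excess is also small against sampling error: at 5%, 8% and 10% with 230 per arm, the standard error √(p(1 − p)/230) is about 1.4, 1.8 and 2.0 points, against excesses of 0.27, 0.54 and 0.87 points, or about 0.6, 1.2 and 2 subjects (excess × 230). Finally, 1 − KM is the display that corresponds to the log-rank test. All of this stands. It limits the weight of the point but does not make the curve an unbiased estimate of the level that Section 5.2.4 takes from it.

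A reader might infer more than the SAP supports:

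- **That the SAP contradicts itself with two Week 16 incidences.** Section 3.2.1 lists incidence and time to discontinuation as separate measures, and no table of a Kaplan-Meier incidence at Week 16 is planned. Only the end of the plotted curve implies one.
- **That the log-rank test is invalid.** It remains a test of the cause-specific hazard of LoE discontinuation.
- **That every listed percentile is wrong.** The 1st and 2nd hardly move, and the 25th is unlikely to be reached at modest rates.
- **That the comparison between arms is distorted.** With the same 10% LoE in two arms, other withdrawals of 10% and 20% would put the curve ends at 10.6% and 11.2%. That needs differential other withdrawal, and nothing in the SAP shows any.

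**Conclusion.** The point holds as a minor one. The planned failure curve, and the percentiles from about the 5th upward where reached, overstate the actual cumulative probability of stopping for LoE and are reached somewhat early. The direction is certain whenever another withdrawal precedes an LoE exit; the size is not, because it rests on assumed rates and constant hazards. For 5-10% LoE with 10-15% other withdrawals it is about 0.3 to 0.9 points at Week 16, and more if other withdrawals are commoner or earlier.

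The log-rank test, the logistic incidence analysis and the Section 6.6 table are unaffected. The endpoint is secondary and lies outside the type I error control of Section 5.1.2, so the primary conclusions do not depend on it.

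**What to change.** In Section 5.2.4 and the matching Appendix 1 row, take the plot and percentiles from the Aalen-Johansen cumulative incidence function for LoE discontinuation, with all other discontinuations before Week 16 as competing events and completers censored at Week 16 as now. Choose the percentiles to show from that function. With completers censored at a common Week 16 point, its final value equals the crude percentage reported with the logistic analysis. Keep the log-rank test, labelled as a test of the cause-specific hazard.

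The cost is one procedure option and a few words in two places. There are two drawbacks: the plot is less familiar, and it shows a different quantity from the one the log-rank test compares, so the figure needs a footnote saying so. If the Kaplan-Meier display is kept, the least that is needed is a label stating that it estimates LoE discontinuation as if no other withdrawals occurred.
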